**Title:** Prefrontal Modulation by Repetitive Bilateral Transcranial Direct Current Stimulation (tDCS) in Crack-Cocaine Inpatients

**Brief Title:** Bilateral Prefrontal Modulation in Crack-Cocaine Addiction (tDCS\_CRACK)

**Institution:** Federal University of Espírito Santo

**Principal Investigator:** [name], PhD

Identifiers: NCT02091167

Unique Protocol ID: tDCS CRACK CEP\_UFES 384281

Secondary IDs: CNPq\_ 475232/2013-5

**Date:** October 23, 2018

Transcranial direct current stimulation (tDCS) is a non-invasive brain stimulation tool which has proven to be efficient in modulating brain activity (George and Aston-Jones, 2010). Previous studies already demonstrated favorable effects of tDCS compared to sham stimulation in substance use disorders and craving. Accordingly, we have demonstrated that in crack-cocaine dependent subjects, five sessions of right anode/left cathode bilateral stimulation of the dlPFC was able to significantly reduce craving both during and after treatment in the real tDCS group as compared to a sham-tDCS group (Batista et al., 2015). Thus, we hypothesized that extension of repetitive bilateral dlPFC tDCS to ten sessions would have a more pronounced effect on craving in crack-cocaine substance use disorder, considering that a successful management of craving during treatment is highly desirable to prevent dropouts and relapses.

## **Material and Methods**

We report this clinical trial according to CONSORT guidelines. This trial was registered under Clinical Trials.gov number NCT02091167.

### *Participants*

All subjects were informed about the purposes of the experiment by the principal investigator and signed a written consent before entering the study.

Thirty-five patients, 29 men and 6 women, who met DSM V criteria for cocaine (crack) use disorder were recruited between June of 2015 and April of 2018 from three specialized clinics for drug use disorder treatment (one public and two private hospitals) from Espírito Santo State, Brazil. They all received standard treatment given by the clinics, consisting of psychosocial approaches – conducted by a professional team of psychologists, nurses, social workers and physicians – sometimes combined with adjunctive pharmacotherapy including benzodiazepines, B-complex vitamins, disulfiram and, if necessary, antidepressants, anxiolytics, antipsychotics, antihypertensive and gastric medication. It must be mentioned that in the public hospital, from where half of the patients was recruited, they were not allowed to have any medication, except non-opioid pain relievers when absolutely necessary, after they had been admitted to the hospital. Therefore, half of the patients were free of medication during the sham- or DC-stimulation. From the other half patients coming from the two private clinics, few of them were medicated (antipsychotics, antidepressants or mood stabilizers) during brain stimulation procedures.

There were two dropouts in the sham-tDCS group that were excluded after randomization. One patient escaped from the treatment facility and the other had to be discontinued because of precocious discharge from the clinic for misconduct.

The inclusion criteria for this study were: (1) male and female patients over the age of 18 years; (2) met criteria for crack-cocaine use disorder according to the ICD-10 Classification of Mental and Behavioral Disorders and the Diagnostic and Statistical Manual of Mental Disorders, fifth edition, as

determined by clinical evaluation; (3) in stable clinical condition with no need for emergency care; (4) able to read, write, and speak Portuguese; and (5) no severe withdrawal signs or symptoms at baseline.

Furthermore, exclusion criteria included: (1) a condition of intoxication or withdrawal due to a substance other than crack-cocaine, (2) unstable mental or medical disorder or substance abuse or addiction other than crack-cocaine use disorder, except nicotine and/or caffeine; (3) diagnosis of epilepsy, convulsions, or delirium tremens during abstinence from crack-cocaine; (4) a previous history of drug hypersensitivity or adverse reactions to diazepam or other benzodiazepines and haloperidol; (5) any contraindication for electrical brain stimulation procedures such as electronic implants or metal implants.

The study was approved by the Brazilian Institutional Review Board of the Federal University of Espírito Santo (CAAE 19403713.6.0000.5060), Brazil, and all patients signed a written informed consent form. The study was conducted in strict adherence to the Declaration of Helsinki and is in accordance with the ethical standards of the Committee on Human Experimentation of the Federal University of Espírito Santo, ES, Brazil.

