### *Craving assessment*

Craving was scored through a brief scale composed of five items (1, 2, 4, 5, and 13) of the Obsessive-Compulsive Cocaine Use Scale, also known as the Obsessive-Compulsive Cocaine Scale (OCCS), which are based on the Obsessive-Compulsive Drinking Scale (Anton et al., 1995;Anton et al., 1996;Anton, 2000), as proposed by Hormes et al. (Hormes et al., 2012) and

Vorspan et al. (Vorspan et al., 2012). These five-item scales assess craving in a narrow sense according to De Wildt et al. (de Wildt et al., 2005).

Through this brief scale it is possible to quantify thoughts and feelings (obsessions), and behavioral intentions (de Wildt et al., 2005), answered on a scale ranging from 0 to 4, resulting in a total score between 0 and 20. Patients are questioned on how much of the time (total per day), when the drug is not used, is occupied by thoughts, ideas, desires, or impulses related to crack-cocaine and its effects; how frequently these thoughts, ideas, desires, or impulses related to crack-cocaine and its effects occur; how much distress or disturbance these ideas, thoughts, impulses or desire related to crack-cocaine use cause when the person is under withdrawal; how much effort they have to make to resist these thoughts, ideas, desires, or impulses, or how much energy they have to spend to think of something else when they enter the mind under withdrawal; and finally ask about their drive to use crack-cocaine.

The OCCS was applied in the week before the beginning of the real or sham-tDCS treatment, during the treatment (second, third and fourth weeks) and in the week after the end of the brain stimulation application, resulting in five time-points measurements.

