### *Statistical Analysis*

We powered the study for a medium effect size based on the results of our previous study (Batista et al., 2015) in which the effect size (partial  $\eta^2$ ) for the main within-subject factor in the respective two-way ANOVA with repeated measures was 0.10384 when comparing craving scores once before, twice during and once after 5-sessions of tDCS (four time-points). The tDCS electrode montage was identical in the studies, and patient populations of crack-cocaine users were similar. We used the correction for SPSS input into the G\*Power 3.1.9.2. With this effect size, for the two-way mixed model ANOVA of the present study with the within factor craving measurements, the

between-subject factor tDCS condition, the dependent variable craving score, and craving measurements x condition interaction as the primary outcome parameter, with a power of 80%, and a two-sided probability of a type I error of 5%, the resulting minimum sample size was 30 participants. To account for waiving or dropouts, which were expected to be very common in this condition, we increased the estimated sample size to approximately 10%, resulting in 33 subjects in total (approximately 16 to 17 subjects in each group).

Most of data (age, patterns of crack-cocaine use, 5-items OCCS) were normally distributed according to the D'Agostino & Pearson normality test, thus they were analyzed by parametric tests. Between-group (sham- and real tDCS) comparisons were conducted by unpaired *Student's t*-tests. For all other non-parametric data (gender, schooling, employment, marital state and tobacco use), Chi-square or Fisher tests were used to compare sham and real tDCS groups.

Besides the two-way ANOVA with repeated measures followed by Bonferroni-corrected t-tests, linear regression analyses were done over craving scores obtained along the 4-week treatment (five time-points measurements) for both groups. Additional comparisons between initial and final OCDS scores were done by paired t-tests for each group, and differences between final and initial scores were compared between sham-tDCS and real tDCS groups with unpaired t-test. Effect sizes were calculated using Cohen's *d* and corrected by Hedges's  $g_s$  for unpaired and Hedges'  $g_{av}$  for paired t-tests (Lakens, 2013).

A two-tailed p-value of 0.05 or less was considered to indicate statistical significance. SPSS Statistics Base 24.0 (SPSS Inc, USA) and GraphPad Prism

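### Two randomised sham patients are excluded, so the primary craving interaction is on the natural reading a completer analysis, and no sensitivity check is planned (minor)

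*Combined protocol and SAP*

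**What the plan says.** The Participants section reports 35 patients recruited and then: "There were two dropouts in the sham-tDCS group that were excluded after randomization". The reasons follow: "One patient escaped from the treatment facility and the other had to be discontinued because of precocious discharge from the clinic for misconduct". Both are events after randomisation, not eligibility failures. Nothing is said of exclusions from the active arm.

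Statistical Analysis names "craving measurements x condition interaction as the primary outcome parameter", tested by a two-way repeated-measures ANOVA on five weekly craving scores. It adds paired initial-versus-final t-tests within each group and a between-group test: "differences between final and initial scores were compared between sham-tDCS and real tDCS groups with unpaired t-test". It also says "linear regression analyses were done over craving scores obtained along the 4-week treatment". It defines no analysis set, no handling of missing craving scores and no sensitivity analysis. Its only provision for dropout is in the sample size: "we increased the estimated sample size to approximately 10%, resulting in 33 subjects in total".

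The opening paragraph gives as part of the rationale that "a successful management of craving during treatment is highly desirable to prevent dropouts and relapses".

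On timing, Procedures describes randomisation after the clinical examination. It then describes about 30 days of regular treatment between admission and the first stimulation. Craving assessment places the first score in the week before stimulation. When the two patients left is not stated.

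**The concern.** The repeated-measures ANOVA needs all five scores, and the change tests need the first and last. With the two patients excluded, these tests use completers only, and every stated omission is from one arm. The linear regressions could use partial series, but they are not the primary test.

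Randomisation supports the comparison of the groups as randomised. It supports the comparison of those who stayed only if leaving is unrelated to the outcome. Craving is the outcome here, and the plan itself says that controlling craving helps to prevent dropout. Blinding to the end of follow-up makes an exclusion driven by known allocation unlikely, but it does not make a patient's departure independent of craving.

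At stake is whether the sign or significance of the primary result depends on two unobserved patients. The number, arm and reasons are disclosed. The timing, the available scores and the effect on the result are not, so a reader cannot check this.

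**Working it through.** **1. The plan's own sample size.** Partial eta-squared is 0.10384, so f² = 0.10384/(1 − 0.10384) = 0.1159. With two groups, five time points, the SPSS convention and sphericity assumed, λ = f² × (N − 2) × 4 on 4 and 4(N − 2) df. At N = 30 power is 0.818, so the stated minimum of 30 reproduces, and 30 × 1.10 = 33. Power is 0.862 at 33 and 0.885 at 35, so losing two patients costs about 2 percentage points.

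**2. Size of the loss.** If the 35 include the two, 35 − 2 = 33, the planned total. The loss is 2/35 = 5.7% overall, and 2/18 = 11.1% or 2/17 = 11.8% of sham, against 0% of active. Arm sizes of 17 and 18 are assumed from the 1:1 ratio. If 35 is the number after exclusion, 37 were randomised and the sham loss is 2/19 = 10.5% or 2/18 = 11.1%.

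**3. Shift in the sham mean.** If the two differ from sham completers by d points in craving change, the sham mean moves by 2d/n, with n the randomised sham total. For d = 4 this is 8/18 = 0.44 or 8/17 = 0.47 points ("resulting in a total score between 0 and 20").

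**4. Effect on the primary interaction.** Assumptions, none of them in the documents:
- completers 16 sham and 17 active, or 15 and 18;
- compound symmetry, with SD of change 3 to 5, so within-subject error variance σ² = SD²/2;
- the group difference Δ and the deviation d both grow linearly from 0 at baseline to full size at the fifth score, giving a sum of squares about the mean of 0.625.

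For completers, h = n_s·n_a/(n_s + n_a) and F = h·Δ²·0.625/(4σ²) on 4 and 124 df. Set F at the chosen p and solve for Δ. Then add the two with their own error, where n_s is the number of sham completers:
- Δ′ = Δ + 2d/(n_s + 2), with d positive if the two did worse;
- h′ = (n_s + 2)·n_a/35;
- SSE = 132σ² + [2n_s/(n_s + 2)]·d²·0.625, on 132 df.

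Example with 16 and 17 completers, SD 5, completer p = 0.05, the two 4 points better:
- F = 2.445, h = 8.242, σ² = 12.5, so Δ = √(4 × 2.445 × 12.5/(0.625 × 8.242)) = 4.87.
- Δ′ = 4.87 − 8/18 = 4.43; h′ = 18 × 17/35 = 8.743; SSE = 1650 + 17.8 = 1667.8.
- F = (8.743 × 4.427² × 0.625/4)/(1667.8/132) = 2.12, p = 0.082.

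Ranges over both splits and SD 3 to 5:

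| The two, against sham completers | Completer p = 0.05 becomes |
|---|---|
| 4 points better | 0.082-0.135 |
| 2 points better | 0.057-0.073 |
| no different | 0.038-0.039 |
| 2 points worse | 0.020-0.027 |
| 4 points worse | 0.011-0.019 |

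A completer p of 0.01 becomes 0.018-0.033 if the two did 4 points better, so it stays significant.

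**5. Where the conclusion changes.** Solving the same equations for a final p of exactly 0.05: a deviation of 4 points better overturns a completer p between about 0.016-0.030 and 0.05. A deviation of 4 points worse turns a completer p between 0.05 and about 0.113-0.167 into a significant one.

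**6. What a mixed model could recover.** Suppose a patient has k scores (baseline plus k − 1 later) and the correlation ρ is 0.3 to 0.7. Under compound symmetry, the share of the final-visit deviation recovered is ρ/(1 + (k − 1)ρ) times the sum of the observed fractions of d. Under AR(1) it is the last observed fraction times ρ to the power of the remaining visits. Across both structures this gives 0% with baseline only, 1-10% with one later score, 5-25% with two and 23-53% with three.

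**The case against.** The strongest reply has four parts.

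- **The only evidence on direction is reassuring.** If poor craving control goes with leaving, the two would have done worse than sham completers. Excluding them then flatters sham and works against tDCS. This stands as a hint. It is a general statement in the rationale, not data on these two patients, so the direction is not established.
- **They may have left before it mattered.** Procedures does not fix the order of randomisation and the roughly 30-day lead-in. The two may have left before any stimulation or craving score, and under blinding such a departure could hardly be an effect of allocation. "Dropouts" and "discontinued" may suggest a later exit, but the documents leave it open. This stands, and is a reason to report the timing.
- **Starting from p = 0.05 is the worst case.** At the planned effect with 33 patients, F = 0.1159 × 31 = 3.59, p about 0.008. The chance that the completer p falls in the range that a 4-point better deviation would overturn is about 5-13%. This stands, conditional on the planned effect being true.
- **The deviation is assumed.** Four points is 0.8 to 1.3 of the assumed SDs, and two points moves p far less. This also stands.

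A reader might go further and infer that the exclusions favour tDCS, that 2 against 0 shows differential dropout, or that the trial lost its power. The documents support none of these. The direction is open. Fisher's exact test gives p = 0.49 for 2/18 against 0/17 and 0.23 for 2/17 against 0/18. The loss is within the planned allowance.

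**Conclusion.** The point holds as a minor one. Two randomised sham patients are left out, the primary and change-score tests are on the natural reading completer analyses, and nothing tests whether this matters. That these are completer analyses is itself inferred, because no analysis set is named.

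The conclusion is at risk only if the completer result lies near 0.05. The document gives no craving results, so whether it does is unknown. The sizes above rest on assumed arm sizes, SD of change, trajectory, correlation and deviation, and on reading the 35 as including the two. A reader might infer that the trial's result is biased or would be reversed. The documents do not support that, only that robustness to these two patients is untested.

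**What to change.** 1. Label the 33-patient ANOVA and the change tests as completer analyses.
2. State when each of the two left, relative to randomisation, first stimulation and first craving score, and which OCCS scores exist.
3. Add a likelihood-based linear mixed model (time, group, time by group) on all randomised patients in their assigned arm, using every available score.
4. Add a shift check. Multiply impute the two patients' missing scores from the sham-arm model, conditional on any scores they have and otherwise from the sham visit means. Shift the imputed scores in 2-point steps in both directions within 0 to 20, and report where the interaction conclusion changes.
5. Label items 3 and 4 as post hoc, since recruitment ended in April 2018 and the document is dated October 2018.

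The cost is one standard model and a short table on data already held. The mixed model assumes missing at random and adds nothing to the interaction if the two have no score after baseline; the shift check then carries the gain. The size of the shifts remains a judgement.

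Statistical Analysis names neither a test nor a denominator for relapse. That gap concerns all patients and should be handled separately.

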### *DC stimulation*

A randomized double-blind clinical trial tDCS protocol was used in the study. Stimulation was done using a DC stimulator (DC-Stimulator Plus, NeuroConn, Ilmenau, Germany) with two carbonated silicone electrodes (35 cm^2) with a thick layer of high-conductive EEG gel beneath them according to our previous study (Nakamura-Palacios et al.,2012). Electrodes were placed

based on the international 10-20 electrode placement system. For tDCS, the cathode was placed over the left dlPFC (F3) while the anode was placed over the right dlPFC (F4). Each session of tDCS lasted for 20 minutes with fade-in and fade-out periods of 30 seconds each. Intensity was set to 2 mA. For sham tDCS, the electrodes were placed at the same positions.

During active tDCS treatment, subjects typically reported tingling sensations under the electrodes area, which rapidly faded (Batista et al., 2015). Our sham intervention was therefore designed to provide an initial period of tingling - the stimulator was automatically switched off after 30 seconds of either anodal or cathodal stimulation - so that similar sensations are perceived during active and sham tDCS protocols, thus serving as an ideal control condition (Nitsche et al., 2003;Gandiga et al., 2006;Batista et al., 2015). Data and instructions in the device display are identical in active and sham settings.

For the sham stimulation procedure, the stimulator automatically switched off after 30 seconds of either anodal or cathodal stimulation yielding sensations typically elicited by tDCS.

### *Craving assessment*

Craving was scored through a brief scale composed of five items (1, 2, 4, 5, and 13) of the Obsessive-Compulsive Cocaine Use Scale, also known as the Obsessive-Compulsive Cocaine Scale (OCCS), which are based on the Obsessive-Compulsive Drinking Scale (Anton et al., 1995;Anton et al., 1996;Anton, 2000), as proposed by Hormes et al. (Hormes et al., 2012) and

Vorspan et al. (Vorspan et al., 2012). These five-item scales assess craving in a narrow sense according to De Wildt et al. (de Wildt et al., 2005).

Through this brief scale it is possible to quantify thoughts and feelings (obsessions), and behavioral intentions (de Wildt et al., 2005), answered on a scale ranging from 0 to 4, resulting in a total score between 0 and 20. Patients are questioned on how much of the time (total per day), when the drug is not used, is occupied by thoughts, ideas, desires, or impulses related to crack-cocaine and its effects; how frequently these thoughts, ideas, desires, or impulses related to crack-cocaine and its effects occur; how much distress or disturbance these ideas, thoughts, impulses or desire related to crack-cocaine use cause when the person is under withdrawal; how much effort they have to make to resist these thoughts, ideas, desires, or impulses, or how much energy they have to spend to think of something else when they enter the mind under withdrawal; and finally ask about their drive to use crack-cocaine.

The OCCS was applied in the week before the beginning of the real or sham-tDCS treatment, during the treatment (second, third and fourth weeks) and in the week after the end of the brain stimulation application, resulting in five time-points measurements.

#### *Relapses in 30- and 60-days follow-up*

After their discharge from the hospital, patients from sham- and real tDCS groups were followed-up for at least 60 days regarding crack-cocaine use relapses. A use relapse was defined as the first episode of return to the

previous uncontrolled pattern of crack-cocaine use (rocks per day) (Klauss et al., 2014). Information about relapse were gathered directly when patients regularly returned to the hospital for clinical follow-up after their discharge and/or by self-report or reports of family members by telephone calls.

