### *Procedures*

Those patients who were eligible according to inclusion and exclusion criteria described above and agreed to participate in this study signed an informed consent sheet. All data were originally acquired from participants entering this single research center clinical trial to investigate the efficacy of tDCS treatment.

After global physical and clinical examination subjects were randomly assigned to one of the two groups (sham- and real tDCS) in a 1:1 ratio using a computer-generated block randomization sequence that was kept with the unblinded study coordinator (not involved in the recruitment). The co-investigator conducting treatments was only given a list of 5-number blinding codes to be loaded to the DC-stimulator before each session of brain stimulation. The device is previously settled with specific settings for the study.

After patients had been admitted to the hospitals, they were maintained under regular treatment for 30 days in average or until they had reached a global clinical stabilization, to have them started in the sham- or real tDCS treatments. The brain stimulation application was then performed in one 20-min session a day, every other day, including weekends, up to a total of 10

sessions, always in the afternoon period, in the following five weeks and they were followed-up after the end of the stimulation treatment for up to 60 days after their discharge from the hospitals.

Craving was measured once a week over five weeks (once before the beginning of the stimulation sessions, three times over the stimulation sessions and once more after the end of stimulation sessions) with a total of five time-points measurements. Relapses were collected after discharge from the hospital up to 60 days after intervention.

Participants and experimenters were blinded for brain stimulation assignments from the beginning of the study protocol up to the end of the 60-days follow-up after the end of sham- or real tDCS treatment, resulting in a double-blind experimental design.

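### Two sham patients excluded after randomisation have no stated place in the relapse outcome, although relapse was already being collected by telephone

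*Combined protocol and SAP*

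**What the plan says.** The relapse section starts observation at hospital discharge: "After their discharge from the hospital, patients from sham- and real tDCS groups were followed-up for at least 60 days regarding crack-cocaine use relapses". Procedures also starts at discharge but ends the window differently: "Relapses were collected after discharge from the hospital up to 60 days after intervention". Elsewhere Procedures describes follow-up lasting at most 60 days from discharge. Information came from return visits to the hospital and/or "by self-report or reports of family members by telephone calls". The relapse definition does not mention patients who leave prematurely.

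On withdrawals, Participants says: "There were two dropouts in the sham-tDCS group that were excluded after randomization". It gives the reasons: "One patient escaped from the treatment facility and the other had to be discontinued because of precocious discharge from the clinic for misconduct". It does not say when, relative to the stimulation course, either patient left.

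Statistical Analysis names the craving-by-condition interaction as primary. It gives no relapse analysis, no analysis population for relapse and no rule for missing relapse status.

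**The concern.** Relapse does not depend on finishing stimulation or on being an inpatient. The plan already had a route that needs neither, yet two patients who left irregularly were excluded and no passage brings them back into the relapse outcome.

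The reasons for exit are not neutral. Escape and expulsion from a crack-cocaine programme are plausibly related to relapse risk, and both exits are in the same arm. An exclusion that is both one-sided and plausibly related to the outcome weakens the protection that randomisation gives the relapse comparison.

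The plan had reason to foresee this. The introduction says "a successful management of craving during treatment is highly desirable to prevent dropouts and relapses", and the sample-size paragraph expects frequent dropout. Premature exit is nevertheless handled only as a ground for exclusion. At stake is whether the 30- and 60-day relapse figures describe the randomised groups or only the patients who were not excluded.

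**Working it through.** **Inputs from the documents.** Recruitment (Participants): "Thirty-five patients, 29 men and 6 women, who met DSM V criteria for cocaine (crack) use disorder were recruited". Two exclusions after randomisation, both sham (Participants). Allocation 1:1 in blocks (Procedures).

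**Not in the documents, so assumed.** Arm sizes, relapse counts, a relapse test, and whether the 35 include the two exclusions. I take 35 randomised and 33 retained, split 16 sham/17 real or 17 sham/16 real.

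**1. The plan's own figure.** There is none for relapse. The only sample size is for craving: f² = 0.10384/(1 − 0.10384) = 0.1159. With N = 30 and five time-points, λ = 0.1159 × 28 × 4 = 12.98 on 4 and 112 df, giving power 0.818. The minimum is 29, or 30 with equal arms, and 30 × 1.10 = 33. Both stated figures reproduce; neither bears on relapse.

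**2. How each patient falls out.**
- Escaped patient: the clock starts at discharge and an escape has no formal discharge, so follow-up has no defined start.
- Patient discharged for misconduct: there was a discharge, so the follow-up wording alone would let this patient in. The exclusion in Participants is what takes the patient out.

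**3. Share lost.** Overall 2/35 = 5.7%. Sham 2/18 = 11.1% or 2/19 = 10.5%. Real tDCS 0%. If the 35 are instead the retained patients, 37 were randomised, and a sham arm of 18 or 19 gives the same percentages.

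**4. Movement in the sham relapse rate.** With r relapses among n retained sham patients and p = r/n, restoring two patients changes the rate by +2(1 − p)/(n + 2) if both relapsed and by −2p/(n + 2) if neither did.

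| Retained sham | Both relapsed | Neither relapsed | Change (points) |
|---|---|---|---|
| 4/16 = 25.0% | 6/18 = 33.3% | 4/18 = 22.2% | +8.3 / −2.8 |
| 8/16 = 50.0% | 10/18 = 55.6% | 8/18 = 44.4% | +5.6 / −5.6 |
| 12/16 = 75.0% | 14/18 = 77.8% | 12/18 = 66.7% | +2.8 / −8.3 |
| 4/17 = 23.5% | 6/19 = 31.6% | 4/19 = 21.1% | +8.0 / −2.5 |
| 8/17 = 47.1% | 10/19 = 52.6% | 8/19 = 42.1% | +5.6 / −5.0 |
| 13/17 = 76.5% | 15/19 = 78.9% | 13/19 = 68.4% | +2.5 / −8.0 |

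**5. Effect on a test.** Two-sided Fisher tests on invented counts, as illustration only:
- 8/16 sham against 4/17 real: p = 0.157 with the exits excluded, 0.086 with both relapsed, 0.289 with neither.
- 10/16 sham against 5/17 real: p = 0.084, 0.044 and 0.176 in the same order.
- All possible count pairs, 17 × 18 = 306 per split: counting both exits as relapsed changes significance at 0.05 in 26 pairs (8.5%) for the 16/17 split and 24 (7.8%) for the 17/16 split. Counting neither as relapsed gives the same 26 and 24.

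**The case against.** The strongest reply is that the documents are silent rather than wrong. Participants reports what happened to two patients. It sets no general rule, does not say which analyses the exclusion covers, and does not say whether relapse calls were attempted. The relapse section speaks of patients from both groups without restricting it to completers. Relapse carries no stated hypothesis, test or sample size. The document is written in the past tense after recruitment closed in April 2018, so new follow-up may be impossible.

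Much of this stands, and it rules out several stronger conclusions that a reader might infer:
- *That the patients left during stimulation, so that stopping stimulation ended follow-up.* The text says only that they were excluded after randomisation. Procedures describes about 30 days of regular treatment before stimulation, and the exits may have come before any session.
- *That the discharge trigger shuts out both patients, or that only regular discharges count.* It leaves only the escaped patient without a start date, and the relapse section does not require a regular discharge.
- *That relapse data for the two are known to be missing.* This follows from the exclusion and is not separately stated.
- *That the sham relapse rate is understated or the benefit of real tDCS exaggerated.* The direction is unknown. If both relapsed, leaving them out lowers sham relapse and is conservative for the trial's hypothesis; if neither did, it is the reverse.
- *That significance turns on these two patients.* That is possible in particular tables but not typical, and the documents give no counts.

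What the reply does not remove is that the stated handling is a post-randomisation exclusion in one arm, for reasons plausibly linked to the outcome, with no provision that restores these patients.

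**Conclusion.** The point holds for the relapse outcome and should be corrected. It is a bias risk in the handling as described as well as a missing detail. Its size is about 11% of sham against 0% of real tDCS, and a sham relapse rate that could shift by up to about 8 percentage points either way. Both figures rest on 35 randomised, 33 retained and the assumed arm split; the second also rests on assumed relapse rates of about 24% to 76%. The documents support neither a direction of bias nor a claim about significance. Relapse is secondary to the craving interaction, whose test this point does not affect.

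**What to change.** Amend Participants, the relapse section and Procedures together:
- Keep every randomised patient in the relapse outcome, whatever the number of sessions received or the route of exit, using the existing telephone and family contacts.
- Define one start date that also applies to patients with no formal discharge. If it is the date of leaving by any route, early leavers start at a different distance from randomisation than others; a date fixed from randomisation avoids that. State the choice.
- Reconcile the three windows: a minimum of 60 days from discharge, a maximum of 60 days from discharge, and a maximum of 60 days from the intervention.
- State whether the 35 include the two exclusions, when each left, and whether relapse was sought.
- Report premature exits by arm, and 30- and 60-day relapse for all randomised patients, with any unreachable leaver counted once as relapsed and once as not relapsed.

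The cost is short edits in three sections and, where contact is still possible, a few calls. If it is not, the two-way bounds and the exits by arm need no new data. The drawbacks are small: some statuses may rest on relatives' reports, and the reported interval is wider.
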